3.5.2 Adverse Events of Special Interest

No adverse events of special interest are identified in the protocol.

3.5.3 Deaths and Treatment Discontinuations due to Adverse Events

A listing of any death will be provided and will include the MedDRA SOC and PT. AEs resulting in permanent discontinuation of investigational product will be summarized by treatment. The summary will include results summarized overall and by MedDRA SOC and PT.

3.5.5 Other Safety Evaluations

3.5.5.1 Vital Signs

Vital signs including pulse rate (beats/min), systolic and diastolic blood pressure (mmHg), temperature (°C), and respiratory rate (breaths/min), as well as their change from baseline will be descriptively summarized by treatment at each visit.

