2 OBJECTIVES AND ENDPOINTS

2.1 Primary Objective(s) and Associated Endpoints

Table 1 Primary Objective(s) and Associated Endpoints

Type	Objective	Endpoint
Safety	Assess the safety and tolerability of MEDI0382 titrated up to the highest clinically tolerated dose (HCTD)	
 • Incidence of treatment-emergent adverse events and treatment-emergent serious adverse events through the end of the up-titration period (up to 8 weeks) and through the end of the follow-up period • Clinically important changes in 12-lead electrocardiogram, vital signs (including heart rate and blood pressure), physical examination, and clinical laboratory evaluations through the end of up-titration period (up to 8 weeks) and through the end of the follow-up period

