3.1.3.2 Dose Escalation Stopping Criteria

Dose escalation will be stopped if the DEC determines that any of the following criteria are met.

- More than 50% of subjects treated with MEDI0382 in a specific dose period experience grade 2 or higher AEs assessed as related to MEDI0382 and require discontinuation of MEDI0382
- One serious adverse event (SAE) occurs in a MEDI0382 subject that is assessed as related to MEDI0382
- Two or more subjects receiving MEDI0382 experiences any of the following:
 - An average absolute (regardless of baseline value) cardiac QTc interval corrected for heart rate by the formula of Fridericia (QTcF) > 500 msec, or an increase of QTcF > 60 msec above the baseline value, confirmed (persistent for ≥ 5 minutes) on a repeat 12-lead ECG
 - Tachycardia, defined as resting supine heart rate > 125 beats per minute persisting for at least 10 minutes (measured at 5 timepoints in the 10-minute period)
 - Symptomatic bradycardia, defined as resting supine heart rate < 40 beats per minute while awake, persisting for at least 10 minutes; or asymptomatic bradycardia defined as resting supine heart rate < 30 beats per minute while awake persisting for at least 10 minutes (measured at 5 timepoints in the 10-minute period)
 - Hypertension, defined as an increase from baseline in resting supine systolic blood pressure (BP) > 40 mmHg or above 180 mmHg and persisting for at least 10 minutes, or an increase from baseline in resting supine diastolic BP > 20 mmHg or above 100 mmHg and persisting for at least 10 minutes
- The above cardiac criteria do not apply if provoked by complicated venepuncture or other vagal provocation

If any of these criteria are met, then the DEC will either:

- Recommend that the study proceed to 3-week treatment extension at the HCTD, or
- Request for review and decision by the MedImmune Safety Review Board on how to proceed or whether to suspend or stop the study

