4.8.4.2 Analysis of Clinical Laboratory Parameters

Laboratory parameters will be assessed at baseline as well as throughout the study. Frequencies of abnormal laboratory measurements will be presented for each laboratory parameter. Also, laboratory parameters will be assessed by presenting tables containing information related to laboratory shifts from baseline relative to the normal range, as well as descriptively over time.

Other safety data such as vital signs, ECG and physical examination findings will be descriptively summarized at each time point by treatment. Mean ambulatory BP and heart rate measurements recorded over 24 hours at different time points will be analyzed using an analysis of covariance model, adjusting for treatment and measurement at baseline.

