3 STATISTICAL METHODS

3.1 General Considerations

Data will be presented in data listings sorted by treatment, dose, subject number, and date collected, where appropriate. Tabular summaries will be presented by treatment arm. Categorical data will be summarized by the number and percentage of subjects in each category. Continuous variables will be summarized with descriptive statistics (eg, n, mean, median, SD, minimum, and maximum).

Analyses will be conducted for each cohort and for the two cohorts combined. Formal statistical modeling analysis for the secondary efficacy endpoints will be conducted for the two-cohort combined analyses. In general, unless stated otherwise, baseline will be defined as the last value prior to dosing.

Two analyses are planned for this study as follows:

- 1 A primary analysis after the up-titration period for Cohort 2, and
- 2 A final analysis after the safety follow-up period for Cohort 2.

Data analyses will be conducted using the SAS[®] System Version 9.4 or higher (SAS Institute Inc., Cary, NC) in a UNIX platform.

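### For vital signs, the SAP's visit-by-visit summaries do not give the number of subjects with a clinically important change over either primary-endpoint window

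*SAP*

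**What the plan says.** Protocol 2.1, Table 1, gives the second primary endpoint as "Clinically important changes in 12-lead electrocardiogram, vital signs (including heart rate and blood pressure), physical examination, and clinical laboratory evaluations", assessed cumulatively over two windows: to the end of up-titration and to the end of follow-up. No definition of clinically important accompanies it.

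SAP 3.5.5.1, which shows no redaction, lists pulse, systolic and diastolic pressure, temperature and respiratory rate, and states that these, "as well as their change from baseline will be descriptively summarized by treatment at each visit". Protocol 4.8.4.2 matches it: "Other safety data such as vital signs, ECG and physical examination findings will be descriptively summarized at each time point by treatment".

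SAP 3.1 adds two general provisions. The first is "Continuous variables will be summarized with descriptive statistics (eg, n, mean, median, SD, minimum, and maximum". The second is "Data will be presented in data listings sorted by treatment, dose, subject number, and date collected, where appropriate".

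Protocol 3.1.3.2 sets limits for individual subjects. Escalation stops if two or more MEDI0382 subjects meet any of several criteria, among them:
- "Tachycardia, defined as resting supine heart rate > 125 beats per minute persisting for at least 10 minutes"
- "Hypertension, defined as an increase from baseline in resting supine systolic blood pressure (BP) > 40 mmHg or above 180 mmHg", with the same persistence requirement
- a diastolic "increase from baseline in resting supine diastolic BP > 20 mmHg or above 100 mmHg and persisting for at least 10 minutes"

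Protocol 4.1.6 uses the same heart rate and blood pressure limits to stop product in an individual subject.

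**The concern.** The endpoint asks whether, and in how many subjects, an important change occurred at any time in a window. The planned output describes the distribution of values at each visit. These are different quantities, and the second does not determine the first. If the SAP is followed exactly, no vital-sign table reports a number of subjects with an important change to the end of up-titration or to the end of follow-up.

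This matters because Protocol 1.6 names tachycardia and altered blood pressure as potential risks, and Protocol 3.2.3.1 describes this as the first study of higher doses in this population. The protocol itself acts on a count of affected subjects when it decides on escalation. Laboratory data, by contrast, receive shift tables in SAP 3.5.4.

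**Working it through.** The plan states no figure for this component, so there is none to reproduce. The check asks whether the planned summaries determine the count.

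**Arm sizes** (Protocol 4.8.2). At 3:1, Cohort 1 has 8 × 3/4 = 6 on MEDI0382 and Cohort 2 has 12 × 3/4 = 9. Combined, that is 15 on MEDI0382 and 5 on placebo.

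**Step 1: what the mean shows.** The shift in an arm mean is k × rise / n, where k is the number of affected subjects. For a systolic rise of 40 mmHg, the boundary of the protocol's limit:
- one subject, combined: 40/15 = 2.67 mmHg
- two subjects at the same visit, combined: 80/15 = 5.33 mmHg
- two subjects at different visits, combined: 2.67 mmHg at each
- one subject, Cohort 2: 40/9 = 4.44 mmHg
- one subject, Cohort 1: 40/6 = 6.67 mmHg

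For a diastolic rise of 20 mmHg in one subject, the combined shift is 20/15 = 1.33 mmHg. The mean dilutes an individual excursion, less so within a cohort.

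**Step 2: what the full set of statistics shows.** The maximum change would reveal a single large rise recorded at a scheduled visit. It does not reveal how many there were. Two constructed sets of 15 systolic changes (mmHg):
- A: −10 (five times), −8, −6, −2, −1, 4, 15, 18, 25, 30, 42
- B: −10 (four times), −8, −3, −3, −2, 4, 4, 5, 8, 18, 42, 42

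Both sum to 67, so both means are 67/15 = 4.47. Both sums of squares are 4459, so both SDs are √[(4459 − 67²/15)/14] = 17.24. Both medians are −2, both minima −10 and both maxima 42. Set A has 1 subject above 40 mmHg (1/15 = 6.7%) and set B has 2 (2/15 = 13.3%).

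**Step 3: across visits.** A maximum change of 42 at each of two visits may be one subject twice or two different subjects. By-visit tables cannot separate these, yet a cumulative endpoint depends on the difference.

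**Step 4: could this arise with 15 subjects?** The documents give no excursion rate, so this uses assumed true rates p. P(at least 1) = 1 − (1 − p)^15. P(at least 2) subtracts a further 15p(1 − p)^14.
- p = 5%: 53.7% and 17.1%
- p = 10%: 79.4% and 45.1%
- p = 20%: 96.5% and 83.3%

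Unless such excursions are rare, one or more affected subjects is likely, and two or more is a realistic outcome.

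**The case against.** A reader might infer that the SAP reports vital signs only as means and so would hide every excursion. The documents do not support that. SAP 3.1 names the minimum and maximum, summaries by cohort are planned, and listings are allowed where appropriate. An extreme reading at a visit would normally be visible.

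A reader might also infer that the whole endpoint component lacks a matching analysis. That does not follow either. Laboratory results have shift tables, and Protocol 4.8.4.2 adds abnormality frequencies. ECGs have normal/abnormal frequencies, and the text after them is redacted. Physical examination findings are to be summarized under Protocol 4.8.4.2, and new clinically relevant ones are reported as adverse events under Protocol 5.4.4.

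Other routes capture some vital-sign events. Protocol 4.1.6 requires product to be stopped at these limits, SAP 3.3.1 counts treatment discontinuations, and SAP 3.5.3 tabulates adverse events leading to discontinuation. These are partial proxies. The visible disposition text does not tie a stop to a vital sign, and excursions not confirmed as persistent would not appear there. Adverse event incidence is a separate primary endpoint, and under Protocol 5.4.4 an asymptomatic excursion becomes an adverse event only on the investigator's judgement.

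Two further points stand as limits on the concern. The protocol limits are escalation and discontinuation criteria and are nowhere called the definition of clinically important. They also require 10 minutes' persistence, while Protocol 4.3.2.4 has blood pressure measured once. Finally, SAP section 1 places table templates in a programming plan that is not among the documents and may contain threshold tables. Even so, the quantity that answers a primary endpoint belongs in the SAP.

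**Conclusion.** The concern holds for vital signs. The planned summaries can show that an extreme value occurred at a visit. They do not give the number of subjects with one over either window, so this part of the primary endpoint is not estimated. The illustrated size is the difference between 1/15 and 2/15 on MEDI0382, which identical planned statistics cannot distinguish.

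This rests on the visible text, the planned 15:5 split and a constructed example. The excursion rates in step 4 are assumptions. No view is taken on whether the clinical limits are right. The trial is small and descriptive and other routes give part of the information, so this is a cheap improvement of minor severity.

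**What to change.** Add one table to SAP 3.5.5.1, by arm, for each cohort and combined, for each of the two windows. It should give the number and percentage of subjects with any post-baseline heart rate, systolic or diastolic reading beyond the limits already in Protocol 3.1.3.2 and 4.1.6. State that the limits serve only as reporting categories and change no clinical rule. Add each subject's worst post-baseline change.

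Show single scheduled readings separately from excursions confirmed as lasting at least 10 minutes, where repeat readings were recorded. Keep the by-visit summaries as support.

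The cost is one table from data already collected; confirmed counts can be given only where repeats exist. The downside is that single readings will flag some transient values, which is why the two kinds must be kept apart.

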3.5.5.2 Ambulatory Blood Pressure Measurements

Mean systolic blood pressure, diastolic blood pressure, and heart rate over the 24-hour collection for 3 periods (awake, asleep, and complete) will be descriptively summarized by treatment at each visit. Mean change from baseline of these parameters will be analyzed using an ANCOVA model adjusting for treatment and baseline value at end of dosing period and treatment extension.

3.5.5.3 Electrocardiogram

Triplicate electrocardiogram (ECG) will be performed using a digitally recorded standard 12-lead electrocardiograph. For each ECG parameter (heart rate, RR, PR, QRS, QT interval, and the derived parameter QT corrected interval QTcF (Fridericia's formula $\frac{QT}{\sqrt[3]{RR}}$), the average of the 3 values will be analyzed. The change from baseline (Day -1) to each post-baseline evaluation will be summarized with descriptive statistics. Results for the qualitative ECG interpretation (normal or abnormal) will be summarized with frequencies and percentages at each evaluation.

[REDACTED]

3.6 Immunogenicity

Analysis of immunogenicity will be based on the Immunogenicity population. The incidence and impact of anti-drug antibody (ADA) to MEDI0382 will be evaluated. The number and percentage of subjects with confirmed positive serum antibodies to MEDI0382 will be

reported by treatment. Titer data and cross-reactivity to glucagon-like peptide 1 (GLP-1) and glucagon (if applicable) will be listed.

The following categories will be utilized to describe the ADA response:

- ADA prevalence: subjects who are ADA positive at any visit (including baseline)
- Subjects who are ADA positive at baseline only
- Subjects who are ADA positive at baseline and positive post baseline
- Subjects who are ADA positive post-baseline only (treatment-induced ADA)
- Proportion of subjects who are treatment-boostered ADA; treatment-boostered ADA is defined as baseline ADA titer that was boosted to a 4-fold or higher level following drug administration
- ADA incidence (treatment-emergent ADA), defined as the sum of treatment-induced ADA (post-baseline positive only) and treatment-boostered ADA

A similar summary will be performed for ADA cross-reactivity to GLP-1 and/or glucagon (as data allows and if applicable).

3.7 Pharmacokinetics

PK parameters will be calculated from plasma drug concentration-time data for MEDI0382 for subjects in the PK population. Descriptive statistics will be generated for PK parameters. However, the results of these analyses will be provided in the bioanalytical report that is prepared by the bioanalyst and pharmacokineticist; therefore, no tables, figures, or listings of PK data will be specified in the SPP.

Actual time of sampling, rather than nominal (planned) sampling time, will be used to derive PK parameters. Nominal sampling time will be used for the summary of PK concentrations and will be utilized in the descriptive summaries in mean and median plots. Missing PK parameters will not be imputed.

The PK parameters will be calculated by standard non-compartmental analysis according to current working practices and using Phoenix 64 or equivalent. All calculations of non-compartmental parameters will be based on actual sampling times.

The following PK parameters of MEDI0382 will be determined, if data allow, for each subject from the plasma concentration-time data:

1. C_{max} : The first occurrence of the maximum observed plasma concentration determined directly from the raw concentration-time data.
2. t_{max} : The first time at which C_{max} is observed will be determined directly from the raw concentration-time data.

3. C_{τ} : trough concentrations from the plasma concentration-time data defined as pre-dose samples.
4. $t_{1/2}$: The apparent terminal elimination half-life obtained as the ratio of $\ln 2/\lambda_z$, where λ_z is the terminal phase rate constant estimated by linear regression analysis of the log transformed concentration-time data.
5. AUC following the last dose until the last measurable concentration (AUC_{0-last}).
6. AUC_{τ} : AUC at the end of the dosage interval τ .
7. R_o : observed accumulation ratio will be calculated using both the AUC and C_{trough} methods, where data allows, as follows: $R_o = AUC_{\tau day i}/AUC_{\tau day 1}$ and $R_o = C_{\tau day i}/C_{\tau day 1}$.

All derived parameters described above will be listed. For each of these parameters, except t_{max} , the following summary statistics will be calculated for each dose group: median, maximum, minimum, arithmetic mean, standard deviation, coefficient of variation (CV), geometric mean. For t_{max} the following summary statistics will be calculated: median, maximum, minimum, arithmetic mean and geometric mean. Individual C_{trough} will be listed by day and will be summarized as maximum, minimum, arithmetic mean, median, and geometric mean.

3.8 Protocol Deviations

A listing of important protocol deviations will be provided.

4 INTERIM ANALYSIS

No interim analyses are planned; however, the DEC will be evaluating the data periodically to determine whether to escalate the dose.

